Advances in risk stratification and therapy, have improved the event-free survival (EFS) and overall survival (OS) for pediatric acute myeloid leukemia (AML) to approximately 50% and 65% respectively, with current treatment strategies. Patients with good response to induction and/or those who lack high-risk cytogenetic and molecular features [classified as low-risk AML (LR-AML)] have even better outcomes with EFS and OS approaching 70% and 85% respectively; however, treatment-related toxicities remain a major concern. Anthracycline-based therapeutic regimens expose patients to the risk of anthracycline-induced cardiotoxicity. Therefore, strategies that reduce cardiac toxicities using tailored approaches while maintaining and/or improving outcomes are needed for all patients with AML. The Children's Oncology Group (COG) regimens AAML1031 and AAML0531 utilized an anthracycline-intensive backbone for LR-AML with cumulative anthracycline doxorubicin-equivalent doses of up to 492mg/m². However, high-risk patients treated with chemotherapy alone received an intensified induction chemotherapy (using mitoxantrone-cytarabine) but with overall reduced doses of anthracycline-equivalent (342mg/m²). We piloted an institutional practice to treat all LR-AML patients with four cycle regimen (Aflac-AML) with the goal of reducing cumulative anthracycline exposure, thereby reducing the risk of cardiotoxicity, while providing three high-dose cytarabine courses. In this pilot institutional experience with this approach, we were able to maintain excellent outcomes for this low-risk group with 3-year event-free survival (EFS) and OS of 70.0% ± 0.1% and 85.5% ± 0.08% respectively, from end of course 1. Recent evolution in cytogenetic classification has further delineated risk groups in AML. Gemtuzumab ozogamicin (GO), an antibody-drug conjugate was shown to reduce relapse risk in patients with CC genotype with de-novo AML on COG study AAML0531. We propose to study the inclusion of gemtuzumab ozogamicin with our Aflac-AML chemotherapy backbone prospectively to validate its use in all pediatric AML and to further evaluate the approach with a cardiac-sparing goal in an expanded experience for low risk AML.

EXPERIMENTAL DESIGN SCHEMA

* Gemtuzumab ozogamicin (GO) dosing to be determined by SNP testing
Risk Stratification – refer Section 4.0

1.0 GOALS AND OBJECTIVES

1.1 Primary Objective

To estimate the event-free survival (EFS) for newly diagnosed patients with pediatric acute myeloid leukemia using a risk stratified approach, including a modified chemotherapy regimen alone for subjects with low-risk features and allogeneic bone marrow transplantation for those with high risk features.

1.2 Secondary Objectives

1. To estimate the overall survival (OS) for newly diagnosed patients with pediatric acute myeloid leukemia
2. To estimate frequency of minimal residual disease (MRD) negative status after one cycle of induction chemotherapy for AML patients who received GO and those that did not receive GO.
3. To estimate the disease-free survival (DFS) for patients who are MRD negative after induction 1, but lack high risk or lowest risk molecular and cytogenetic features as currently classified
4. To estimate the incidence of early and late cardiotoxicity in patients with de novo AML that receive the four-cycle Aflac-AML regimen with the inclusion of dexrazoxane
5. To estimate the frequency of infection and/or febrile neutropenia by chemotherapy regimen

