Pollard et al divided all patients on AAML0531 based on their CD33 expression into quartiles. Patients with high CD33 expression (Q2-4) had significantly improved EFS and relapse risk²⁴. Single nucleotide polymorphisms (SNPs) in CD33 (specifically resulting in increased number of T alleles) showed a positive correlation with poorer response to GO-containing regimens²⁵. On the COG AML pilot study AAML 03P1, coding SNPs in CD33 (rs35112940 and rs12459419) were associated with better risk disease and improved outcomes compared to other genotypes²⁶. Further characterization and testing in a larger cohort of patients on AAML0531 (n=816) showed that patients with CC genotype (rs12459419) have a significant response to GO as compared to CT or TT genotypes²⁷. When genotyping data was correlated with expression, it was found that the presence of T allele (CT/TT) genotype strongly correlates with low expression of CD33. There are 256/816 patients (31%) who had either CT or TT genotype and were in the high expression (Q2-4) group on AAML0531. In this group, addition of GO did not improve relapse risk. Conversely, there were 61/816 individuals (7%) who were CC genotype that showed low quartile (Q1) CD33 expression. The RR even in this small group was still improved significantly with GO through the p-value was just shy of statistical significance (p=0.055)²⁷. While determination of CD33 expression is universally possible with routine multi-dimensional flow cytometry, division of the data acquired into quartiles that are validated and can be compared between institutions is challenging. Given that the CD33 genotyping shows strong correlation with relapse risk regardless of CD33 expression, we will be obtaining CD33 genotyping on all patients at the time of diagnosis. We expect the turn-around time for this testing to be approximately 4-5 days, allowing for a single 3 mg/m² dose of GO to be administered between days 6-10 during Induction I for patients with CC genotype.

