5.1 Induction 1 – ADE (10+3+5) with GO

The following therapy guidelines are for patients during Induction I. Patients on Induction I will receive gemtuzumab in addition to ADE therapy based on GO genotyping. Induction I lasts a total of 28 days.

Intrathecal Cytarabine: IT

Given at time of diagnostic lumbar puncture or Day 1.

Age-based dosing:

Age (yrs)	Dose
0-0.99	20 mg
1-1.99	30 mg
2-2.99	50 mg
≥ 3	70 mg

For CNS positive patients: add twice weekly IT AraC doses until CNS is clear, plus two additional treatments. A minimum of four intrathecal treatments are to be administered during the period of three weeks following diagnosis.

Cytarabine: Slow IV Push (e.g., over 1-2 minutes)

100 mg/m²/dose (3.3 mg/kg/dose if BSA < 0.6 m²) every 12 hours (total of 20 doses) on Days 1-10.

Daunorubicin (DAUN): IV over 15 minutes

50 mg/m²/dose (1.67 mg/kg/dose if BSA < 0.6 m²) every other day (total of 3 doses) on Days 1, 3, 5.

See Section 6 if direct bilirubin is > 2.

Etoposide (ETOP): IV over 60 – 120 minutes

100 mg/m²/dose (3.3 mg/kg/dose if BSA < 0.6 m²) daily (total of 5 doses) on Days 1-5.

See Section 6 if direct bilirubin is > 2.

Gemtuzumab Ozogamicin (GO): IV over 2 hours

3 mg/m²/dose (0.1 mg/kg/dose if BSA < 0.6 m²) once (total of 1 dose) on Day 6 through 10.

GO to be given once when GO genotyping demonstrates CC genotype. It can be given on any day between days 6-10 of Induction 1.

Pre-medicate with an antihistamine such as diphenhydramine, 1 mg/kg IV (max 50 mg), acetaminophen 10-15 mg/kg PO (max 650 mg) and methylprednisolone (1mg/kg) PO/IV. Repeat every 4 hours as needed to prevent post infusion complications.

Following Induction I, the next course (Induction II) starts on Day 29 or when blood count parameters and clinical condition are acceptable (whichever occurs later). This should not precede the end of course marrow exam.

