11.1 STATISTICAL CONSIDERATIONS

Sample size: This is a pilot study aimed at utilizing a risk-stratified approach along with pharmacogenomics to treat newly diagnosed patients with AML. Annually we expect to have 10-20 de novo AML patients to be diagnosed and treated at our institution. This two-year study would be expected to enroll approximately 30 patients (both low and high risk) during that time period. As a pilot study, this trial is not hypothesis-driven but rather estimation-driven, and the sample size is based on a feasible two-year target for our institution.

Descriptive statistics will be conducted for demographic and patient characteristic variables, including toxicity related variables. Mean and standard deviation will be used for continuous variables and frequency and percent will be used for categorical variables.

Primary Endpoints:

1. Event-free survival: Event-free survival (EFS) is defined as the time from on study to death, failure to achieve remission or relapse, where those patients who do not experience these events will be censored at last follow-up date. EFS will be estimated using the Kaplan-Meier method for newly diagnosed patients with pediatric acute myeloid leukemia using a risk stratified approach.

Secondary Endpoints:

1. Disease-free survival: Disease-free survival (DFS) from end of first course of therapy is defined as time from end of first course of therapy to death or relapse, where those patients who do not experience these events will be censored at last follow-up date. DFS will be estimated using the Kaplan-Meier method for newly diagnosed patients with pediatric acute myeloid leukemia using a risk stratified approach.
2. Overall survival: Overall survival (OS) is defined as (1) time from study entry and (2) from end of first course of therapy to death, where those who do not die will be censored at

last follow-up date. OS will be estimated using the Kaplan-Meier method for newly diagnosed patients with pediatric acute myeloid leukemia using a risk stratified approach.

3. Minimal residual disease: Minimal residual disease (MRD) is the proportion of patients that are in remission (MRD negative) after one cycle of induction chemotherapy in both the GO and non-GO groups. Descriptive statistics (frequency and percent) will be used to estimate the frequency of MRD.

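### MRD negativity is to be reported by whether GO was received, although GO follows CD33 genotype and can be given only from Day 6; the groups should be defined by genotype, with a stated denominator

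*Combined protocol and SAP*

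**What the plan says.** Section 1.2, objective 2, sets out to estimate the frequency of MRD-negative status after one induction cycle "for AML patients who received GO and those that did not receive GO". That is grouping by receipt. The Endpoints list after Section 1.3 and secondary endpoint 3 in Section 11.1 are looser. Section 11.1 speaks of remission "after one cycle of induction chemotherapy in both the GO and non-GO groups" and does not say whether these groups mean dose received or genotype.

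Assignment is by genotype. Section 5.1 states "GO to be given once when GO genotyping demonstrates CC genotype" and adds "It can be given on any day between days 6-10 of Induction 1". Section 5.2 repeats both rules for FLT3-ITD patients, who also take sorafenib on Days 11-28 of the same course. On timing, Section 2.2 says "We expect the turn-around time for this testing to be approximately 4-5 days".

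The planned analysis is "Descriptive statistics (frequency and percent) will be used to estimate the frequency of MRD". The analysis set in Section 11.1 (eligible, at least one dose) is specified for the primary efficacy analysis. No denominator is given for MRD, and no rule covers a patient who dies before the end-of-course marrow or has no evaluable result. Nor does any section say where a CC patient who does not get GO is counted.

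**The concern.** Receipt of GO is known only some days into treatment. A CC patient who dies before Day 6, or is too ill for the dose on Days 6-10, cannot enter the received-GO group and by the wording of objective 2 falls into the other one. If such patients are mostly failures, the GO group loses failures and the non-GO group gains them, whatever GO does. This is the familiar bias from classifying patients by something that happens after treatment starts.

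The opening summary says the trial is meant to validate the use of GO in pediatric AML, and MRD is the only efficacy endpoint the plan splits by GO. The two percentages will therefore be read against each other even though no formal contrast is planned. The number of patients in question is small, but so are the groups.

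**Working it through.** **Sample size (the plan's own figure).** Two years at 10-20 patients per year gives 20-40, midpoint 30. This agrees with the approximately 30 in Section 11.1.

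**Group sizes (assumption).** Section 2.2 gives, of 816 genotyped AAML0531 patients, 256 CT/TT in CD33 expression quartiles 2-4 and 61 CC in quartile 1. If quartile 1 holds 816/4 = 204 patients, CT/TT in quartile 1 = 204 - 61 = 143 and CT/TT in total = 256 + 143 = 399 (49%). CC is then 816 - 399 = 417 (51%), and 30 x 0.51 = 15.3, so about 15 and 15. The quartiles may have been cut on a wider set of patients. If quartile 1 held 20% to 30% of the 816 (163 to 245), CC = 621 - quartile 1 = 458 to 376, or 56% to 46%: about 17 to 14 of 30.

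**Illustration with no GO effect.** The documents give no MRD-negative rate, so 10/15 in each genotype is an assumption. Suppose one patient of each genotype dies before Day 6 and 10 of the other 14 are MRD negative.

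| Rule | GO or CC | Non-GO or CT/TT | Gap |
|---|---|---|---|
| By receipt, early death counted as not MRD negative | 10/14 = 71.4% | 10/16 = 62.5% | +8.9 points |
| By receipt, patients without MRD excluded | 10/14 | 10/14 | 0 |
| By genotype, all treated patients | 10/15 | 10/15 | 0 |

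The first row needs only one CC failure to miss GO; how the five CT/TT failures arise does not matter. With two or three such CC failures it becomes 10/13 v 10/17 (77% v 59%, 18 points) or 10/12 v 10/18 (83% v 56%, 28 points).

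**Other rates.** Let p be the MRD-negative rate among Day 6 survivors, with one early death per genotype counted as a failure. Receipt grouping gives p v 14p/16. For p = 0.5 to 0.8 the gap is +6.2 to +10.0 points. If the only early death is in a CC patient, the comparison is p v 15p/16, a gap of +3 to +5 points. In that case genotype grouping is not zero either: at p = 0.7 it gives 9.8/15 = 65.3% v 70%, or -4.7 points. That is a chance imbalance in deaths, not one produced by the grouping rule.

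**Alive but not dosed.** Let one CC patient miss the dose and have MRD-negative probability q, with p = 0.7. The non-GO rate is (0.7 x 15 + q)/16.

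- q = 0.35: 67.8%, gap +2.2 points
- q = 0.70: 70.0%, gap 0
- q = 0.90: 71.3%, gap -1.3 points

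**How many such patients.** The documents give no rate of death before Day 6 and no missed-dose rate. The only mortality figures are 1% and 5% for the whole of induction in SWOG S0106 (Section 2.2), taken here as an upper range for death before Day 6. Among 15 CC patients:

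- Expected deaths: 15 x 0.01 = 0.15 to 15 x 0.05 = 0.75
- At least one, 1 - (1 - d)^15: 14% to 54%
- At least two, subtracting 15d(1 - d)^14 as well: 1% to 17%
- At least three: about 0.04% to 3.6%

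**Sampling error for scale.** At 15 v 15 and p = 0.7, the 95% half-width of a difference is 1.96 x sqrt(2 x 0.7 x 0.3/15) = 0.328, about 33 points.

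**The case against.** The strongest reply is that this is a descriptive pilot. Two percentages are reported, no test or contrast is planned, and Section 11.1 calls the study estimation-driven. This stands: the risk lies in how the figures are read side by side, not in a planned comparison.

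The early-death route also depends on an open choice. A patient who dies before Day 6 has no end-of-course marrow. If patients without MRD are excluded, receipt grouping adds nothing beyond genotype grouping. That stands too, and it is a reason to state the denominator in advance.

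Several stronger readings are tempting, and the documents do not support them.

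- *Section 11.1 groups by receipt.* Only objective 2 does; Section 11.1 and the Endpoints list leave the groups undefined.
- *This is the only planned result on GO.* The interim table in Section 11.1 separates ADE from ADE+GO for infection and hematologic recovery, and objective 5 estimates infection by regimen.
- *Any missed dose favors GO.* A late laboratory result is not shown to be prognostic. With a turnaround of 4-5 days and a window to Day 10, it should also be uncommon.
- *CC patients are known to be better risk.* Section 2.2 says the CD33 SNPs "were associated with better risk disease and improved outcomes compared to other genotypes" but does not name the favorable genotype. Confounding is possible, its direction is not stated, and genotype grouping would not remove it.

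A further split by low-risk marker, high-risk marker or neither is not worth adding, since 30/(2 x 3) leaves about 5 patients per cell.

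**Conclusion.** The point holds as a fault in how the MRD groups are defined. Objective 2 uses a post-treatment classification when a baseline one is available, and no section settles where undosed CC patients go or who is in the denominator. With one affected patient the spurious gap is about 9 points in the illustration, and 3 to 10 points over the assumed rates when the patient is an early death counted as a failure. This rests on a split near 15 v 15, undosed CC patients doing worse, and patients without MRD being retained.

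A reader might take the 18- and 28-point gaps as the expected size. They are not. They require two or three undosed CC patients, all failures, which is unlikely at the mortality figures in the documents. Even the 9-point gap is well inside the sampling error of about 33 points. That limits the consequence but does not justify a systematic error that costs almost nothing to remove.

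**What to change.** In objective 2, the matching item in the Endpoints list, and secondary endpoint 3 of Section 11.1:

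1. Define the groups by CD33 genotype: CC (GO planned) and CT/TT (GO not planned), with patients never genotyped on their own line.
2. Use all eligible treated patients as the denominator, and count early death or no evaluable end-of-Induction-I marrow as not MRD negative.
3. Report how many CC patients did not receive GO, and why. Give the by-receipt table as supportive only.
4. List sorafenib-treated FLT3-ITD patients separately, because sorafenib precedes the same marrow. At the roughly 15% FLT3 mutation rate in Section 2.4 this is at most about 0.15 x 30 = 4.5 patients.
5. State that the CC v CT/TT difference does not estimate the GO effect, because genotype and GO coincide.

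The cost is a change of wording. Section 8.1 already schedules CD33 genotype at baseline and MRD at the end of each course; one data field for the reason GO was omitted may be needed. The CC rate may look slightly less favorable. For example, if true rates were 80% with GO and 60% without, one undosed CC patient would give (0.8 x 14 + 0.6)/15 = 78.7%, so the difference would be 18.7 points, not 20. Treatment and sample size are unaffected.

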1.3 Exploratory Objectives

To describe the prevalence of molecular abnormalities in de-novo AML samples using comprehensive genomic testing.

ENDPOINTS

Primary Endpoints include the event-free survival defined as the time from on study to death, failure to achieve remission or relapse

Secondary Endpoints include

- disease-free survival (DFS) from end of first course of therapy, defined as time from end of first course of therapy to death or relapse
- overall survival defined as time from study entry and from end of first course of therapy
- proportion of patients that are in remission (MRD negative) after course 1 in both the GO and non-GO groups
- Disease-free survival for patients who are MRD negative but lack high or low risk molecular and cytogenetic features, defined as time from end of first course of therapy to death or relapse
- Estimate the proportion of patients that develop cardiac ejection fraction <50% (CTCAE V5.0 grade 2 or greater dysfunction) either during therapy (early cardiotoxicity) or after completion of therapy (late cardiotoxicity)
- Estimate the proportion of patients who develop infection and/or febrile neutropenia during each treatment course
- Estimate the effect of infection and/or febrile neutropenia on duration of hospital admission for each treatment course

Exploratory Endpoints include descriptive analysis of molecular abnormalities in de-novo AML.

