7.0 SUPPORTIVE CARE

7.1 General Guidelines

The following guidelines are intended to give general direction for optimal patient care and to encourage uniformity in the treatment of this study population. We will follow our institutional guidelines for management of hospitalization and discharge for these patients.

Hospitalization/Hospital Environment

Hospitalization following each course of chemotherapy is strongly recommended until the absolute phagocyte count (sum of the neutrophils, bands and monocytes) is rising for 2 successive days, and the patient is afebrile and clinically stable.

It is recommended that patients should be assigned to rooms with special air filtration systems such as high efficiency particulate air filters (HEPA) or clean-air rooms with constant positive pressure airflow if at all possible.

Central Venous Access

It is recommended that all patients have a double lumen central venous access line placed prior to the beginning of therapy.

Hyperleukocytosis and Metabolic Derangement

Patients with high peripheral blast counts (> 100,000/ μ L) may have increased problems related to metabolic abnormalities, bleeding, and hyperviscosity. Transfusion with packed red blood cells should be given very cautiously, since it may increase viscosity and increase the risk of leukostasis. In these patients, the platelet count should be maintained at least greater than 20,000/ μ L

Continuation of AML Therapy

AML therapy can proceed when there is documented evidence of response to antimicrobial therapy for infections complications, absence of fever or other signs or symptoms of infection, and other starting criteria have been met.

Nutrition

Active measures should be used to prevent weight loss of greater than 10% of pre-illness body weight. If possible, enteral feedings are preferred to parenteral.

Mucosal Evaluation and Care

Mucositis is expected and may be severe; liberal use of pain medications for this condition is encouraged. For patients with poor oral hygiene, consultation by dentistry is recommended prior to initiating therapy.

Suppression of Menstruation

Menstruating females may receive depo-injections or another suppressant during the entire course of this protocol per institutional standards.

Irradiation

Blood products should be irradiated following the current FDA guidelines found at:

<http://www.fda.gov/cber/gdlns/gamma.htm>

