4. Disease-free-survival MRD negative: Disease-free-survival, defined as time from end of first course of therapy to death or relapse, will be estimated for MRD negative patients who lack high or low risk molecular and cytogenetic features using the Kaplan-Meier method.
5. Cardiac ejection fraction: Descriptive statistics (frequency and percent) will be used to estimate the frequency of patients that develop cardiac ejection fraction <50% (CTCAE V5.0 grade 2 or greater dysfunction) either during therapy (early cardiotoxicity) or after completion of therapy (late cardiotoxicity).

Exploratory Endpoints:

1. Molecular abnormalities: Descriptive statistics will be used to describe the molecular abnormalities seen in de-novo AML samples using comprehensive genomic testing.

Analysis Datasets:

All eligible patients who receive at least one dose of protocol therapy will be included in the primary efficacy analysis. Safety analysis will be conducted using the Safety Population, defined as any participant receiving at least one dose of study treatment.

Interim Analysis:

The rates of infectious and hematologic toxicities with each chemotherapy course are well established from prior COG study AAML0531 (refer to table below). These toxicity rates will be monitored after enrollment of the first 10 patients and subsequently after the next 10 patients are enrolled. While this is highly unlikely to happen, if toxicity rates are exceeding those expected for each course, the study will be stopped.

AAML0531	ADE	ADE +GO	MA	AE	Capizzi
Infection incidence					
Documented infection	35 %	36 %	69%	49 %	67%
Neutropenic fever	31 %	32 %	23%	23 %	18%
Hematologic Recovery (days)					
Median time to platelets >50K	26	28	38	25	42
Median time to ANC >500	30	30	37	27	40

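### The infection-on-hospital-stay endpoint has no analysis in Section 11.1, and the one general rule that fits it would give a comparison biased, on average, towards longer stays with infection

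*Combined protocol and SAP*

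**What the plan says.** The endpoint list after Section 1.3 has two infection endpoints. One is a proportion per course. The other is an effect: "Estimate the effect of infection and/or febrile neutropenia on duration of hospital admission for each treatment course". The matching objective, item 5 of Section 1.2, concerns frequency only.

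Section 11.1 gives an analysis for five secondary endpoints: disease-free survival, overall survival, MRD status, disease-free survival in a subset of MRD-negative patients, and ejection fraction. Neither infection endpoint is among them. What remains is a general statement, "Descriptive statistics will be conducted for demographic and patient characteristic variables, including toxicity related variables", followed by "Mean and standard deviation will be used for continuous variables and frequency and percent will be used for categorical variables".

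Section 7.1 describes what ends a stay: "Hospitalization following each course of chemotherapy is strongly recommended until the absolute phagocyte count" has been rising for two days. The patient must also be free of fever and stable.

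The interim-analysis table in Section 11.1 gives reference rates from the earlier cooperative-group trial, for example "Documented infection 35 % 36 % 69% 49 % 67" (percent, for ADE, ADE+GO, MA, AE and Capizzi in that order).

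**The concern.** The endpoint asks how much infection prolongs admission, and infection occurs during the admission. Whether a patient was ever infected is known only once the stay is over, and patients who stay longer have more days in which to become infected. A contrast of ever-infected with never-infected patients therefore shows longer stays in the first group even when infection changes nothing.

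Two features of Section 7.1 add to this. Slow count recovery prolongs the stay and plausibly also the period of infection risk. The fever condition for discharge makes part of any association automatic.

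At stake is a declared secondary endpoint. With nothing specified, an analyst would most naturally tabulate mean stay by infection status and report the difference as the effect.

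**Working it through.** The plan states no figure for this endpoint, so there is nothing to reproduce. The check asks what an ever/never comparison would return if infection had no effect.

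**Inputs from Section 11.1**
- Documented infection, p: 35%, 36%, 69%, 49% and 67% for ADE, ADE+GO, MA, AE and Capizzi.
- Median days to ANC >500: 30, 30, 37, 27 and 40, used as a stand-in for mean stay μ. This is an assumption, because Section 7.1 ties discharge to a rising phagocyte count and not to this threshold.

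**Assumptions not in the documents**
- Stays follow a gamma distribution with coefficient of variation (CV) 20% to 40%.
- Infection risk is either constant through the stay or confined to days 7–21.

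**Constant risk.** With daily hazard λ and a gamma stay, the uninfected share is (1 + λμCV²)^(−1/CV²) = 1 − p. Mean stay in the uninfected is μ/(1 + λμCV²) = μ(1 − p)^(CV²). Since μ is the weighted mean of the two groups,

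false difference = μ[1 − (1 − p)^(CV²)] / p.

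- ADE+GO, CV 20%: 0.64^0.04 = 0.9823, so 30 × 0.0177 / 0.36 ≈ 1.5 days.
- MA, CV 40%: 0.31^0.16 = 0.8291, so 37 × 0.1709 / 0.69 ≈ 9.2 days.

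**Risk on days 7–21 only.** The infection probability for a stay T is π(T) = 1 − exp{−λ·max(0, min(T, 21) − 7)}. λ is solved so that the mean of π equals p. The difference is E[Tπ]/E[π] − E[T(1 − π)]/E[1 − π], evaluated numerically.

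| Course | Constant risk, CV 20% to 40% (days) | Days 7–21 only, CV 20% to 40% (days) |
|---|---|---|
| ADE | 1.5 to 5.7 | 0.1 to 2.0 |
| ADE+GO | 1.5 to 5.7 | 0.1 to 2.0 |
| MA | 2.5 to 9.2 | 0.0 to 2.1 |
| AE | 1.5 to 5.6 | 0.3 to 2.9 |
| Capizzi | 2.6 to 9.7 | 0.0 to 1.6 |

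**Sensitivity to the distribution.** Log-normal stays with the same medians and constant risk give 1.0–1.2 days at an SD of 5 days, 1.9–2.3 at 7, 3.7–4.4 at 10 and 6.8–7.8 at 14.

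**Sensitivity to the exposure.** The endpoint also counts febrile neutropenia ("Neutropenic fever 31 % 32 % 23% 23 % 18"). If the two table rows are mutually exclusive, which is an assumption, the rates sum to 66%, 68%, 92%, 72% and 85%. The constant-risk formula then gives larger values in every course, for example 3.9 to 13.4 days for MA. With risk confined to days 7–21, the log-normal version reaches 4.1 days (AE, SD 14).

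**Does a time-dependent analysis remove the bias?** On simulated no-effect data (SD 5, 7 and 10 days), a Cox model for discharge with infection as a time-varying covariate gave hazard ratios of 0.94–1.08, which is noise around 1. The ever/never covariate on the same data gave 0.51–0.86, a false delay in discharge.

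**Precision.** With 30 patients, k of them infected, and an SD of 7 days, the standard error of a difference in means is 7√(1/k + 1/(30 − k)). This is 2.6 days for AE (k = 15). It is 5.1 days for MA on the summed rates (k = 28, leaving two patients event-free).

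**The case against.** The strongest reply is that the documents never say mean stays will be compared by infection status. The mean-and-SD sentence is a rule for summarising variables, not a contrast. A reader might infer that the plan as written will report a positive effect of several days in every course whether or not one exists. The documents do not support that, for three reasons.

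- The plan as written specifies no analysis, so it returns no estimate.
- The bias is an average tendency. In no-effect trials of 30 patients under constant risk, the naive difference was negative in roughly a fifth to just over a quarter of simulations at a CV of 20%, and in about one in eight or fewer at 40%.
- Several days requires both wide variation in stay and risk that continues through it. If risk falls in an early window that nearly all patients complete, the bias nearly vanishes at a CV of 20%.

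All of this stands, and it limits the claim.

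It is also true that a time-dependent analysis does not cure everything. Confounding by prolonged neutropenia and the fever condition for discharge both survive it. The trial is an estimation-driven pilot, the matching objective covers frequency only, and no stopping rule depends on this endpoint. These facts limit the consequences. They do not supply an analysis for an endpoint that is worded as an effect.

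**Conclusion.** The point holds as a gap with a predictable hazard. A declared effect endpoint has no analysis, and the only rule that fits would, if applied by infection status, give a comparison biased upward on average. With documented-infection rates and no true effect, the bias is about 1.5 to 10 days under constant risk and about 0 to 3 days if risk is confined to days 7–21, for a CV of stay between 20% and 40%. Those ranges rest on an assumed spread of stay, an assumed timing of infection, and recovery time as a proxy for stay. The trial's own data could fall anywhere within them or, with a narrower spread, below them. This should be corrected, but it does not affect the primary endpoint.

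**What to change.** Add a paragraph to Section 11.1 for this endpoint that:

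- analyses time to discharge separately for each course, with first infection or febrile neutropenia as a time-dependent exposure, by a Cox model with a time-varying covariate or an admission–infection–discharge multistate model that yields extra days;
- defines the start and end of a stay, and says how a patient already infected or febrile at the start is classified;
- treats death and transfer to transplant as competing ends of stay;
- states that confounding by prolonged neutropenia, and the part of the association built in by the fever condition for discharge, remain;
- reports raw mean stays by infection status as description only, not as an effect.

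The cost is that paragraph, modest programming, and the use of infection onset and discharge dates, which Section 8.2 does not list by name. Estimates will be imprecise with about 30 patients, with fewer in later courses as high-risk patients leave for transplant (Section 5.3). In some courses few discharges will occur without a prior event. Intervals should therefore be reported and the result called exploratory.
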